2 INTRODUCTION

2.1 Background

Target Disease

Chronic Tympanic Membrane Perforation (CTMP) is defined as stable maintenance of tympanic membrane perforation over 3 months, in contrast to acute tympanic membrane perforations, which heal within 7 to 10 days [Seonwoo et al, 2013]. CTMP affects both pediatric and adult patients and can result from disease, trauma, or medical procedures. Due to the continuous opening in the tympanic membrane, chronic perforation is usually attributed to chronic inflammation in the middle ear, resulting in suppurative otitis media [Seonwoo et al, 2013; Aggarwal et al, 2006]. Surgical repairs such as myringoplasty or tympanoplasty are employed and are currently the main treatments for patients with CTMP. Successful tympanic membrane closure rates vary between studies, ranging from 35% to 99% [Aggarwal et al, 2006]. Disadvantages associated with these surgical procedures include anesthesia-associated risks and the inconvenience of surgery. Therefore, a non-invasive treatment is desired in order to address the unmet need.

ASP0598 and Its Pharmacological Concept

Preclinical studies revealed that proliferation and migration of keratinocytes across layers of the tympanic membrane facilitate closure of the perforation site during the healing process [Santa Maria et al, 2010a]. Keratinocyte proliferation and migration are essential to cutaneous wound healing, and wound stimuli induce keratinocyte shedding of epidermal growth factor (EGF) receptor ligands in vitro, particularly the ligand HB-EGF [Tokumaru et al, 2000]. HB-EGF (an 87 amino acid glycoprotein) is a member of the EGF family of proteins that is encoded by the HB-EGF gene. Preclinical studies showed that HB-EGF was upregulated by over 8-fold by 12 hours following perforation of the tympanic membrane and remained upregulated for a prolonged time compared to constantly expressed EGF in rats [Santa Maria et al, 2010b]. Thus, HB-EGF appears to play a crucial role in tympanic membrane wound healing after acute tympanic membrane perforation. In a study [Santa Maria et al, 2015a], KB-R7785, which inhibits HB-EGF expression, was administered for 1 week to mice with tympanic membrane perforation (CTMP animal model); persistent tympanic membrane perforation longer than 3 months was observed in these mice. In addition, single topical administration of recombinant mouse pro-heparin-binding EGF-like growth factor with a sustained-release dose via a bioabsorbable chitosan-based polymer to the CTMP animal model showed complete closure of tympanic membrane perforation in 83.3% of animals, while application of other growth factors, such as EGF and fibroblast growth factor 2, healed only 15.8% and 31.6%, respectively, of the tympanic membrane perforations in the animal model [Santa Maria et al, 2015a]. These data from the literature suggest that topical, non-invasive administration of HB-EGF is a potentially effective treatment for patients with CTMP.

ASP0598 Otic Solution contains recombinant human heparin-binding EGF-like growth factor that is diluted with a buffered aqueous solution to adjust the dose strength and mixed with a

polymeric solution to enable the formation and retention of hydrogel after administration into the ear.

2.1.1 Nonclinical and Clinical Data

Detailed information can be found in the Investigational Brochure (IB).

Pharmacology

ASP0598 enhanced the proliferation of primary human and mouse epidermal keratinocytes with half-maximal effective concentrations (EC₅₀) of 11.72 and 52.92 ng/mL, respectively.

A single dose of topical application of ASP0598 Otic Solution (0.04 µg/mL to 5 µg/mL as final concentrations of ASP0598) onto a perforated tympanic membrane increased the healing rate, meaning that ASP0598 Otic Solution increased the number of animal ears with complete perforation closure in a mouse model of CTMP. The minimum efficacious concentration in this model was 0.2 µg/mL.

Pharmacokinetics

The toxicokinetics of ASP0598 were assessed in mice and cynomolgus monkeys. After a single administration into the external auditory canal or transtympanic administration of ASP0598 Otic Solution at concentrations of 15 µg/mL and 150 µg/mL, there was no discernible absorption of ASP0598. Administration of [⁸⁹Zr]ASP0598 Otic Solution toward tympanic membranes in cynomolgus monkeys followed by positron emission tomography (PET) scans showed the presence of residual [⁸⁹Zr]ASP0598 Otic Solution around the tympanic membranes from 0 to 14 days after administration. Radioactivity in all plasma samples collected from these same animals was at background levels.

Toxicology

The safety of ASP0598 Otic Solution has been evaluated in 8 good laboratory practice (GLP) toxicity studies in CBA/CaJ mice and cynomolgus monkeys: 2 pivotal, extended single-dose toxicity studies following administration into the external auditory canal and 2 pivotal, single-dose ototoxicity studies following transtympanic administration, 2 pivotal, repeat-dose toxicity studies following administration into the external auditory canal and 2 pivotal, repeat-dose ototoxicity studies following transtympanic administration.

Single dose administration of ASP0598 Otic Solution into the external auditory canal of either mice or cynomolgus monkeys resulted in no adverse findings or observations at concentrations up to 150 µg/mL. These results were confirmed following transtympanic administration of ASP0598 Otic Solution in both species. However, non-adverse, minimal to moderate procedure and/or vehicle related, histopathological changes were observed in cynomolgus monkeys following a single dose administration of ASP0598 Otic Solution into the external auditory canal or transtympanically.

Administration of ASP0598 Otic Solution to mice by the external auditory canal or transtympanically resulted in serum concentrations of HB-EGF near or below the limit of quantification, while in cynomolgus monkeys, ASP0598 Otic Solution administration

resulted in serum concentrations of HB-EGF that remained at baseline values. These data indicate that the external auditory canal or transtympanic route of administration of ASP0598 Otic Solution was not associated with discernible systemic exposure to HB-EGF.

Based on these results, no observed adverse effect level (NOAEL) was set at the highest concentration of 150 µg/mL in both the mouse and cynomolgus monkey studies following single external auditory canal or transtympanic administration.

Finally, results from 4 GLP repeat dose toxicity studies in mice and cynomolgus monkeys were comparable with the results from the single dose administration assessments. In these studies, ASP0598 Otic Solution was administered either into the external auditory canal or transtympanically 3 times at 2-week intervals. No test article-related adverse effects were noted in either species when ASP0598 Otic Solution was applied either into the external auditory canal or transtympanically to the middle ear. For both mice and cynomolgus monkeys the repeat dose results indicated that the NOAEL was also 150 µg/mL.

Clinical Studies

As of the date of the preparation of this protocol, no clinical studies of ASP0598 have been conducted. Therefore, the safety profile of ASP0598 Otic Solution has not been established.

2.1.2 Summary of Key Safety Information for Investigational Product(s)

Given the limited safety information with ASP0598, there are currently no expected serious adverse reactions for ASP0598. Detailed reference safety information (RSI) can be found in the IB.

2.2 Study Rationale

This is the first clinical trial for ASP0598 Otic Solution. Surgical procedure is the only available treatment for CTMP and includes anesthesia-associated risks and the inconvenience of surgery. ASP0598 Otic Solution will be developed as a non-invasive treatment in order to address the unmet need. This study will be a randomized, placebo-controlled and investigator and subject blinded study to evaluate the safety, tolerability, efficacy and pharmacokinetics in subjects with CTMP.

2.3 Risk Benefit Assessment

The non-clinical profile of ASP0598 Otic Solution demonstrates its potential efficacy on tympanic membrane perforation, localized distribution at the administration site with no systemic exposure to HB-EGF, and a favorable safety profile, supporting its clinical investigation. In this study, skin local reaction in the external ear canal will be assessed after topical application of ASP0598 Otic Solution. An appropriate administration to the tympanic membrane and observation of administration site are required to minimize exposure to the middle ear. In addition, monitoring of auditory functions (otology examinations) is recommended.

Overall, the risk associated with the participation of subjects with CTMP in this study is considered acceptable.

3 STUDY OBJECTIVE AND ENDPOINTS

3.1 Primary Objective and Endpoints

| Objective | Endpoints |
|--|--|
| 
To evaluate the safety and tolerability of ASP0598 Otic Solution | 
Treatment-emergent adverse events (TEAEs)Incidence of adverse events of special interest as defined below:
Cholesteatoma or ear neoplasmOtotoxic symptoms (tinnitus, sensorineural hearing loss, dizziness)Otitis media or otitis externaChange from baseline in bone conduction hearing at 1, 2, 4 kHz by Pure Tone Audiometry (PTA)Change from baseline in Tinnitus Visual Analog Scale (TVAS) |

3.2 Secondary Objective and Endpoints

| Objective | Endpoints |
|--|--|
| 
To evaluate the efficacy of ASP0598 Otic Solution 
For secondary efficacy endpoints the hypothetical strategy will be applied.
 | 
Efficacy
 
Single Dose
 
Complete closure of Tympanic Membrane Perforation (TMP) at Week 8 for Single Ascending Dose (SAD) and at Week 12 for dose expansionChange from baseline in the ratio of TMP size per total area of tympanic membrane at Week 8 for SAD and at Week 12 for dose expansionChange from baseline in TMP size at Week 8 for SAD and at Week 12 for dose expansion 
Multiple Dose:
 
Complete closure of TMP at Week 12 for Multiple Ascending Dose (MAD) and at Week 16 for dose expansionChange from baseline in the ratio of TMP size per total area of tympanic membrane at Week 12 for MAD and at Week 16 for dose expansionChange from baseline in TMP size at Week 12 for MAD and at Week 16 for dose expansion |

For the dose expansion, hypothetical strategy will be applied to analyze the secondary endpoints. Details of intercurrent events (ICEs) and estimand are shown below.

3.2.1 Intercurrent Events

The following ICEs may happen:

- Treatment discontinuation due to any reason
- Study discontinuation due to any reason

3.2.2 Treatment regimen under evaluation

Randomized treatment administered as directed per Schedule of Assessments.

3.2.3 Estimand

Population: defined by the appropriate inclusion/exclusion criteria in the protocol.

Efficacy endpoints:

1. Complete closure of TMP at Week 12 for single dose expansion and Week 16 for multiple dose expansion.
2. Change from baseline in the ratio of TMP size per total area of tympanic membrane at Week 12 for single dose expansion and Week 16 for multiple dose expansion.
3. Change from baseline in TMP size at Week 12 for single dose expansion and Week 16 for multiple dose expansion.

Strategy for addressing ICEs: hypothetical strategy will be used to estimate the outcome at Week 12 for single dose expansion and Week 16 for multiple dose expansion.

Population-level summary:

- **Endpoint #1:** difference in proportion of subjects with complete closure of TMP at Week 12 for single dose expansion and Week 16 for multiple dose expansion between ASP0598 Otic Solution and placebo.
- **Endpoint #2:** difference in mean change from baseline in the ratio of TMP size per total area of tympanic membrane at Week 12 for single dose expansion and Week 16 for multiple dose expansion between ASP0598 Otic Solution and placebo.
- **Endpoint #3:** difference in mean change from baseline in TMP size at Week 12 for single dose expansion and Week 16 for multiple dose expansion between ASP0598 Otic Solution and placebo.

Data that will be used for the analysis:

- **Endpoint #1:** data necessary for this analysis is complete closure status at Week 12 for single dose expansion and Week 16 for multiple dose expansion. For the subjects who have discontinued treatment or the study before these data are collected due to ICEs, the complete closure status just before the ICE will be used as the status at Week 12 for single dose expansion and Week 16 for multiple dose expansion.
- **Endpoints #2 and #3:** data necessary for these analyses are TMP size per total area of tympanic membrane and TMP size at each visit, respectively. For the subjects who have discontinued treatment or the study before these data are collected due to ICEs, only data obtained before the ICE will be used in the mixed model repeated measures (MMRM) to handle discontinued subjects in some sense if the subjects remained in the study under missing at random (MAR) assumption.

3.3 Exploratory Objectives and Endpoints

| Objective | Endpoints |
|--|--|
| To evaluate otological parameters that may correlate with efficacy outcome and pharmacokinetics of ASP0598 Otic Solution | 
Single Dose:
 
 • Complete closure of TMP for post baseline visits at Day 2, Day 3*, Week 1, Week 2, Week 4 for SAD and Week 2, Week 4, and Week 8 for dose expansion • Change from baseline in the ratio of TMP size per total area of tympanic membrane for post baseline visits at Day 2, Day 3*, Week 1, Week 2, and Week 4 for SAD and Week 2, Week 4, and Week 8 for dose expansion • Change from baseline in TMP size for post baseline visits at Day 2, Day 3*, Week 1, Week 2, and Week 4 for SAD and Week 2, Week 4, and Week 8 for dose expansion 
 * Day 3 evaluations will only be performed for cohorts 1, 2 and 3. 
Multiple Dose:
 
 • Complete closure of TMP for post baseline visits at Week 1, Week 2, Week 3, Week 4, Week 5, and Week 8 for MAD and Week 2, Week 4, Week 6, Week 8, and Week 12 for dose expansion • Change from baseline in the ratio of TMP size per total area of tympanic membrane for post baseline visits at Week 1, Week 2, Week 3, Week 4, Week 5, and Week 8 for MAD and Week 2, Week 4, Week 6, Week 8, and Week 12 for dose expansion • Change from baseline in TMP size for post baseline visits at Week 1, Week 2, Week 3, Week 4, Week 5, and Week 8 for MAD and Week 2, Week 4, Week 6, Week 8, and Week 12 for dose expansion 
Single and Multiple Dose:
 
 • Time to closure of TMP • Size of TMP $\leq 5\%$ of pars tensa surface area after treatment • Size of TMP $\leq 1\%$ of pars tensa surface area (pin point perforation) after treatment • Change from baseline in air bone (A-B) gap by PTA • Change from baseline in air conduction hearing by PTA • Percentage improvement from baseline in A-B gap by PTA $\geq 50\%$ (improvement of conductive hearing) • Improvement from baseline in air conduction hearing by PTA ≥ 15 dB • A-B gap after treatment was 15 dB or less • Air conduction hearing threshold after treatment was 30 dB or less • Type of tympanogram (A, B or C) • Equivalent ear canal volume (ECV) by tympanometry 
Pharmacokinetics
 
 • Serum concentration of ASP0598 (dose escalation part only) |

Table continued on next page

| Objective | Endpoints |
|---|---|
| To evaluate the safety of ASP0598 Otic Solution | 
• Vital signs (body temperature, blood pressure and pulse rate) |

4 STUDY DESIGN AND DOSE RATIONALE

4.1 Study Design

This is a randomized, placebo-controlled and investigator and subject blinded study to evaluate the safety, tolerability, efficacy and pharmacokinetics in subjects with CTMP.

The main part of this study is dose escalation. Dose escalation will start with single ascending dose (SAD) followed by multiple ascending dose (MAD, Q2W x3).

Dose escalation will primarily assess safety and tolerability of single dose and multiple doses of ASP0598 Otic Solution. Dose escalation will consist of up to 4 cohorts for SAD and up to 2 cohorts for MAD, with different dose levels ([Table 6](#)). Each cohort will consist of 5 subjects (ASP0598 Otic Solution n = 4 and placebo n = 1) for SAD and 8 subjects (ASP0598 Otic Solution n = 6 and placebo n = 2) for MAD.

Single and/or multiple dose expansion will be opened based on the safety and efficacy results following an interim analysis. Single dose expansion will be opened based on the results of the first interim analysis, which will occur after the completion of SAD. Data will be summarized for all time points available. Multiple dose expansion will be opened based on the results of the second interim analysis, which will occur after the completion of MAD.

Table 6 Planned Dose Levels for Dose Escalation

| Cohort | Dose regimen | Dose (µg) | Drug concentration (µg/mL) | Administration volume (mL) | ASP0598 Otic Solution (n) | Placebo (n) |
|---------------|---------------------|-------------------|-----------------------------------|-----------------------------------|----------------------------------|--------------------|
| 1 | Single | 0.03 | 0.2 | 0.15 | 4 | 1 |
| 2 | Single | 0.15 ^a | 1.0 ^a | 0.15 | 4 | 1 |
| 3 | Single | 0.75 ^a | 5.0 ^a | 0.15 | 4 | 1 |
| 4 | Single | 2.25 ^a | 15 ^a | 0.15 | 4 | 1 |
| 5 | Q2W×3 | 0.75 ^a | 5.0 ^a | 0.15 | 6 | 2 |
| 6 | Q2W×3 | 2.25 ^a | 15 ^a | 0.15 | 6 | 2 |

^a Planned dose levels, doses may be adapted depending on emergent safety and tolerability data.

This study will consist of the following:

Single Dose:

- Screening (Days -28 to -1)
- Randomization (Day 1)
- Observation [through Day 57 (SAD) or through Day 85 (single dose expansion)]

Multiple Dose:

- Screening (Day -28 to -1)
- Randomization (Day 1)
- Observation [through Day 85 (for MAD) or through Day 113 (for multiple dose expansion)]
- Additional Treatment on Days 15 and 29

Prior to any study-related assessments, the Informed Consent Authorization Form will be signed by the subject at Screening (Visit 1). All subjects will enter into a screening period (Days -28 to -1) and will be evaluated for randomization eligibility after completing screening procedures. Eligible subjects will be randomized on Day 1 (Visit 2).

For a subject with bilateral TMP, once both ears have been identified as meeting all inclusion/exclusion criteria at Randomization on Day 1 (Visit 2), the ear with the worse hearing will be selected as the treated ear, unless a rationale exists to treat the other ear. In the case of equivalent hearing level in both ears, the investigator will decide the treatment side with subject and will document the reason in the source document and the eCRF. In the case that the investigator is unable to decide the appropriate ear to treat, consultation with the sponsor may be required.

Dose Escalation

Approximately 20 subjects for SAD and 16 subjects for MAD will be enrolled in dose escalation part of the study. The initiation and selection of dose concentrations for MAD will be based on at least 3 cohorts of SAD.

For SAD, after randomization on Day 1, subjects will receive ASP0598 Otic Solution or placebo administration into the affected ear. Subjects will return to the investigative site for assessments on Days 2, 3, 8, 15, 29, and 57 [End of Study (EOS)]. Day 3 evaluations will only be performed for cohorts 1, 2 and 3.

For MAD, after randomization on Day 1, subjects will receive ASP0598 Otic Solution or placebo administration into the affected ear and will receive additional treatments into the same ear on Days 15 and 29. Subjects will return to the investigative site for assessments on Days 8, 15, 22, 29, 36, 57, and 85 (EOS).

For SAD and MAD, subjects who terminate early from the study will complete EOS assessments.

For MAD only, Subjects who discontinue treatment will be encouraged to complete all protocol defined study visits through the Day 85 (EOS).

The decision to escalate or stop escalation during SAD will be made by the Dose Escalation Committee (DEC). The DEC will operate as per the approved DEC Charter.

The DEC will decide dose escalation and the initiation and selection of doses for MAD cohorts based on the emerging safety and tolerability data from SAD. The tentative starting

dose concentration of MAD will be 5.0 µg/mL, and another dose concentration up to a maximum feasible dose concentration of 15 µg/mL will be considered.

The first interim analysis will be conducted after completion of the last SAD cohort. Data will be summarized for all time points available. The second interim analysis will be conducted after completion of the last MAD cohort.

The Data Monitoring Committee (DMC) will review the data and make the final decision to open single and/or multiple dose expansion. The DMC operation, roles and responsibilities will be described in the DMC Charter.

Subjects may be replaced at the discretion of the sponsor. If replaced, the replacement subject will be given the same treatment group the original subject's randomized treatment group.

Dose Expansion

The decision to open single and/or multiple dose expansion will be made based on the safety and efficacy results of the interim analyses after completion of SAD and after completion of MAD by the DMC per the charter. Once the decision to open single and/or multiple dose expansion is made, the number of treatment groups (2 or 3 treatment groups including 1 or 2 active treatment groups and 1 placebo group) and the dose for ASP0598 Otic Solution will be selected based on the safety and efficacy result of the interim analyses. All analyses will be described in the Interim Analysis Plan (IAP).

Up to 39 subjects will be randomized to single dose and/or multiple dose expansion. Based on the interim analysis results:

- If 3 treatment groups are selected, approximately 39 subjects will be randomized in a 1:1:1 ratio of high dose ASP0598 Otic Solution, low dose ASP0598 Otic Solution, or placebo (13 subjects in each treatment group).
- If 2 treatment groups are selected, approximately 26 subjects will be randomized in a 1:1 ratio of high dose ASP0598 Otic Solution or placebo (13 subjects in each treatment group).

Stratification at the time of randomization will be based on the % size of the TMP at the screening visit and subjects will be balanced equally between the treatment groups. Dose expansion will assess safety and efficacy of ASP0598 Otic Solution.

Single Dose Expansion

After randomization on Day 1, subjects will receive ASP0598 Otic Solution or placebo administration into the affected ear at the investigative site. Subjects will return to the investigative site for assessments on Days 15, 29, 57, and 85 (EOS).

Subjects who terminate early from the study will complete EOS assessments at the time of discontinuation.

Multiple Dose Expansion

After randomization on Day 1, subjects will receive ASP0598 Otic Solution or placebo administration into the affected ear. Subjects may receive additional treatment in the same

ear on Days 15 and 29. Subjects will return to the investigative site for assessments on Days 15, 29, 43, 57, 85 and 113 (EOS).

In cases where complete closure is confirmed on Day 15 or Day 29, the subject will not receive the next scheduled dose(s), but will complete all visit assessments as defined in the Schedule of Assessments through Day 113.

Subjects who terminate early from the study will complete EOS assessments at the time of discontinuation.

Subjects who discontinue treatment will be encouraged to complete all protocol defined study visits through the Day 113.

In single dose expansion and/or multiple dose expansion, subjects may be replaced at the discretion of the sponsor. If replaced, the replacement subject will be given the same treatment group the original subject's randomized treatment group.

4.1.1 Decision Process for Dose Escalation, Dose Escalation Stopping Rules and Definition of the Maximum Tolerated Dose

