6.6 Dose Modification

SAD and single dose expansion

Not Applicable.

MAD

On Day 15 or Day 29, treatment can be skipped at the Investigator's discretion based on safety reasons that interrupt IP administration (e.g., ear canal skin irritation, mild otorrhea). Subjects should be encouraged to return to the office for evaluation and additional IP administration within the Day 15 or Day 29 visit windows. In the case that the investigator is unable to conduct IP administration for anything other than safety reasons, consultation with the sponsor may be required.

Multiple dose expansion

The statement above for MAD is also applicable to the multiple dose expansion. Additionally, the treatment on Day 15 or Day 29, treatment will be skipped in cases where complete closure is confirmed. If the perforation is detected on Day 29 after treatment was skipped on Day 15, IP administration can be conducted.

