6.3 Study Drugs Exposure and Compliance

Actual dose of study drug will be summarized using descriptive statistics, entire planned volume of study drug administered (Yes, No), was there needle stick or injury during study

drug administration (Yes, No), area of injury (Ear Canal Skin, Tympanic membrane, Other) and multiple dose phase only: total number of doses administered (1, 2 and 3) will be summarized using number and percentage of subjects for the SAF by treatment group.

Actual dose of study drug (μg) = Administration concentration ($\mu\text{g}/\text{mL}$) x Actual volume of study drug (mL).

Administration concentration values for each dose are provided in Table 1 of the protocol.

Imputed date for study drug dose date may be used (Section [6.9.3.3](#)).

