6.5.1 Adverse Events

AEs will be coded using MedDRA.

For the AEs, the following summaries will be presented:

- An overview of TEAEs and deaths
 - Number of TEAEs
 - Number and percentage of subjects with TEAEs
 - Number of drug-related TEAEs
 - Number and percentage of subjects with drug-related TEAEs
 - Number of serious TEAEs
 - Number and percentage of subjects with serious TEAEs
 - Number of serious drug-related TEAEs
 - Number and percentage of subjects with serious drug-related TEAEs
 - Number of TEAEs leading to treatment discontinuation (MAD and MDE only)

- Number of deaths
- Number and percentage of subjects with TEAEs by SOC and PT for the following:
 - 1) TEAEs
 - 2) Drug-related TEAEs
 - 3) TEAEs Leading to Treatment Discontinuation (MAD and MDE)
 - 4) Serious TEAEs and including number of events
 - 5) Drug-related serious TEAEs and including number of events
 - 6) Common ($\geq 15\%$ in any treatment group) TEAEs for expansion only
 - 7) TEAEs excluding serious AEs and including number of events and number of threshold events. Here threshold equals 5%. This summary will be created only if at least one serious TEAE is present.
- An overview of TEAEs of interest
 - Number of TEAEs of interest
 - Number and percentage of subjects with TEAEs of interest
 - Number of drug-related TEAEs of interest
 - Number and percentage of subjects with drug-related TEAEs of interest
 - Number of serious TEAEs of interest
 - Number and percentage of subjects with serious TEAEs of interest
 - Number of serious drug-related TEAEs of interest
 - Number and percentage of subjects with serious drug-related TEAEs of interest

The above summary will present results for any TEAEs of interest and each of the TEAEs of interest: Cholesteatoma or neoplasm, Ototoxic symptoms (tinnitus, sensorineural hearing loss, dizziness) and Otitis media or otitis externa.

- Number and percentage of subjects with TEAEs of special interest by SOC and PT for the following:
 - 1) TEAEs of special interest for Cholesteatoma or neoplasm
 - 2) TEAEs of special interest for Ototoxic symptoms (tinnitus, sensorineural hearing loss, dizziness)
 - 3) TEAEs of special interest for Otitis media or otitis externa
 - 4) Serious TEAEs of special interest for Cholesteatoma or neoplasm and including number of events
 - 5) Serious TEAEs of special interest for Ototoxic symptoms (tinnitus, sensorineural hearing loss, dizziness) and including number of events

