6.5.4 Microscopic Ear Examination

On Day 1, Week 2 (multiple dose only) and Week 4 (multiple dose only), 1 hour after the treatment, number and percentage of subjects will be used to summarize the following canal reactions of treated ear by treatment group:

- Did the Ear experience an abnormal ear sensation
 - No
 - Yes
 - Burning
 - Stinging
 - Itching
 - Pain
 - Other

Percentages for the subcategories of 'Yes' will be based on number of subjects with abnormal ear sensation=Yes.

- After Day 1, for categorical endpoints status of the middle ear and status of the treated tympanic membrane, number and percentage of subjects will be used to summarize baseline value and post-baseline value at each specified post-baseline analysis visit by treatment group. Other parameters will be listed only.

Status of the treated tympanic membrane (Normal, Abnormal, Abnormal: Myringitis, Abnormal: Hematoma, Abnormal: Other, Not visible)

Status of the middle ear in the treated ear (Normal, Abnormal, Abnormal: Mucosal inflammation with effusion, Abnormal: Mucosal inflammation without effusion, Abnormal: Other, Not visible)

Percentages for the subcategories of 'Abnormal' will be based on number of subjects with abnormal.

Analysis visits:

SAD	Day 2, Day 3*, Week 1, Week 2, Week 4, Week 8 and EOS
Single dose expansion	Week 2, Week 4, Week 8, Week 12 and EOS
MAD	Week 1, Week 2, Week 3, Week 4, Week 5, Week 8, Week 12 and EOS
Multiple dose expansion	Week 2, Week 4, Week 6, Week 8, Week 12, Week 16 and EOS

*Day 3 evaluations will only be performed for cohorts 1, 2 and 3.

Number and percentage of subjects will be used to summarize the local skin reaction at the application site by grade as assessed by Modified Brighton Grading Scheme.

- Day 1 post dose through end of study visit by grade, grade 1 or above, grade 3 or above
- Day 1 post dose by grade, grade 1 or above, grade 3 or above
- Day 2 by grade, grade 1 or above, grade 3 or above (SAD only)
- Day 3 by grade, grade 1 or above, grade 3 or above (SAD cohorts 1, 2 and 3 only)
- 2nd dose: post dose through end of study by grade, grade 1 or above, grade 3 or above (MAD and multiple dose expansion)
- 2nd dose: post dose on the dosing day by grade, grade 1 or above, grade 3 or above (MAD and multiple dose expansion)

- 3rd dose: post dose through end of study by grade, grade 1 or above, grade 3 or above (MAD and multiple dose expansion)

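### In multiple dose expansion the number of applications depends on closure, so the whole-period TEAE and AESI tables do not show tolerability at equal exposure; a first-application table should be added

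*Protocol*

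**What the plan says.** - **Skip rule.** Protocol 4.1, Multiple Dose Expansion: "In cases where complete closure is confirmed on Day 15 or Day 29, the subject will not receive the next scheduled dose(s". Visits continue through Day 113 regardless. Protocol 6.6 repeats that "treatment will be skipped in cases where complete closure is confirmed", and adds: "If the perforation is detected on Day 29 after treatment was skipped on Day 15, IP administration can be conducted".
- **Contrast with MAD.** Protocol 4.1 says MAD subjects "will receive additional treatments into the same ear on Days 15 and 29". Protocol 6.6 lets a MAD dose be skipped for safety reasons but has no closure-based skip.
- **TEAE window.** One window per subject, from first administration through the end of study visit (Protocol 9.5.1). SAP 6.9.1 closes it in this part at the earlier of the end of study day and Day 113, plus 7 days.
- **TEAE and AESI tables.** SAP 6.5 presents safety by treatment group. SAP 6.5.1 plans "Number and percentage of subjects with TEAEs by SOC and PT for the following" a list of TEAE types, and also counts of events. No TEAE or AESI table is split by dose interval or by doses received, or expressed per application.
- **Dose count.** SAP 6.3 tabulates "total number of doses administered (1, 2 and 3" by arm, but no safety table uses it.
- **Local reactions.** SAP 6.5.4 has a Brighton row for "2nd dose: post dose through end of study by grade, grade 1 or above, grade 3 or above", the same for the third dose, and rows for Day 1 post dose, Days 2 to 18, and Day 19 onward.
- **Inference.** Safety is descriptive, with no hypothesis test (Protocol 9.5).

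**The concern.** Exposure in this part follows from the outcome that the drug is meant to cause. An arm that closes ears early receives fewer applications over the same follow-up.

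The documents treat each application as carrying some local risk. Needle injury is tabulated (SAP 6.3), ear sensation and Brighton grade are recorded after each dose (SAP 6.5.4), and canal irritation and otorrhea are reasons to skip a dose (Protocol 6.6). In the nonclinical data, "minimal to moderate procedure and/or vehicle related, histopathological changes were observed in cynomolgus monkeys"; the Protocol calls these changes non-adverse and reports them after a single dose, so they support plausibility only.

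Safety and tolerability is the primary objective, and multiple dose expansion, if opened, is the largest placebo-controlled repeat-dose part. A lower TEAE percentage on ASP0598 could be read as good tolerability when part of it reflects fewer applications.

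**Working it through.** **1. The plan's own figures.** Protocol 9.1 assumes closure of 10% on placebo and 80% on the higher concentration, two-sided 0.05. Exact Fisher power at 11 per group is 90.5%, which matches the stated figure of more than 90%. 11 / 0.90 = 12.2, so 13 per group. Both reproduce. These closure rates are for the end of the part and say nothing about Day 15 or Day 29.

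**2. Applications per subject.** Let p be the closure rate, and F15 and F29 the shares of eventual closers confirmed closed by Day 15 and Day 29 (assumed). Ignoring safety skips, dropout and re-opening:

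mean applications = 1 + (1 − p·F15) + (1 − p·F29)

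| F15, F29 | Active (p = 0.80) | Placebo (p = 0.10) | Ratio |
|---|---|---|---|
| 0, 0 | 3.00 | 3.00 | 1.00 |
| 0.25, 0.50 | 2.40 | 2.92 | 0.82 |
| 0, 1 | 2.20 | 2.90 | 0.76 |
| 0.50, 1 | 1.80 | 2.85 | 0.63 |
| 1, 1 | 1.40 | 2.80 | 0.50 |

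The plan's closure rates are therefore compatible with anything from equal exposure to half.

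**3. Effect on subject incidence.** Let f1, f2 and f3 be the shares receiving 1, 2 and 3 applications, with an independent risk q per application:

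incidence = 1 − [f1(1−q) + f2(1−q)² + f3(1−q)³]

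Assumptions: q = 0.15 in both arms; placebo closed by Day 15/Day 29 in 5%/10%; active in 20%/40%, 40%/60% or 60%/80%.

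- Placebo: 1 − [0.05(0.85) + 0.05(0.7225) + 0.90(0.6141)] = 36.9%; mean applications 2.85.
- Active 20/40: 1 − [0.20(0.85) + 0.20(0.7225) + 0.60(0.6141)] = 31.7%; mean 2.40.
- Active 40/60: 1 − [0.40(0.85) + 0.20(0.7225) + 0.40(0.6141)] = 27.0%; mean 2.00.
- Active 60/80: 1 − [0.60(0.85) + 0.20(0.7225) + 0.20(0.6141)] = 22.3%; mean 1.60.

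Solving for the active q that gives the placebo incidence, a true per-application ratio of about 1.19, 1.43 or 1.75 would appear as no difference. With 13 per arm the incidences are 4.8 placebo subjects against 4.1, 3.5 or 2.9 active.

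Using step 2's timing, a placebo risk of 10% per application and a true per-application ratio of 2.0, the whole-period ratio is 1.80 with three doses each. It is 1.53, 1.47, 1.24 and 1.01 in the last four rows of the table.

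**4. The reverse error.** If events do not depend on repeat applications, whole-period incidence is undistorted and events per application mislead: 2.85/2.40 = 1.19, 2.85/2.00 = 1.43 and 2.85/1.60 = 1.78 against active, with no drug effect.

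**5. The Brighton rows.** The second- and third-dose rows contain only ears treated again, which are mainly those still open and so are selected differently by arm. The Days 2 to 18 row takes the worst grade in the interval. In this part that includes the Day 15 application and its grading 60 minutes later (Protocol Table 5), which only re-treated ears have. The Day 1 post-dose row is a clean randomised comparison.

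**The case against.** Much of the opposing case stands.

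- **The whole-period comparison is valid for the regimen.** Treatment is to stop once the ear has closed, and both arms are followed to Day 113. A reader might infer that the planned tables are biased. They are not, for that regimen; per-application tolerability is a different question.
- **The direction is conditional.** A reader might infer that the tables always flatter ASP0598. That fails where risk does not accrue with each application, such as first-dose reactions or intercurrent illness.
- **Timing is not in the documents.** A reader might infer from 80% against 10% that active subjects must receive clearly fewer applications. Those rates carry no Day 15 or Day 29 timing, and a ratio of 1.0 is possible.
- **More is planned than subject percentages.** SAP 6.5.1 includes event counts. Day 1 Brighton, ear sensation after each dosing visit (SAP 6.5.4) and a Day 2 to Week 2 TVAS summary (SAP 6.5.3) already address early tolerability.
- **Other repeat-dose evidence exists.** MAD has no closure skip and gives 12 active and 4 placebo subjects (two cohorts of 6 and 2). Protocol 2.1.1 reports repeat-dose animal results comparable with single-dose results.
- **Precision is low** at 13 per arm, and safety is descriptive.

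None of this supplies a TEAE or AESI comparison over an interval with equal application counts, or removes the selection in the later Brighton rows.

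**Conclusion.** The point holds in a limited form. Application count in multiple dose expansion depends on closure, and the plan has no TEAE or AESI table at equal exposure. If active ears close more often by Day 15 or Day 29 and risk accrues per application, the whole-period tables understate the active/placebo per-application ratio.

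The size rests on assumptions: 37% placebo against 22% to 32% active with no drug effect, at 15% risk per application and the timing in step 3. It is nil if no closure is confirmed by Day 29. In the extreme case of step 2, a true two-fold per-application risk shows as about 1.0.

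A reader might also infer that a per-application rate should replace the planned tables. Step 4 shows why it should not: its denominator depends on closure too. The balanced comparison is the first interval, when every treated subject has had exactly one application.

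**What to change.** For multiple dose expansion only, in SAP 6.5.1 and 6.5.4:

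1. Keep all planned tables.
2. Add TEAEs, drug-related TEAEs and AESIs by arm, with onset from the first application to before any second application, or to the Day 15 visit if that application is skipped. Add a convention for events starting on the day of the second application; the before/after-dose check box in SAP 5.1 is described for Day 1 only.
3. End the early Brighton interval at the same point instead of Day 18. Table 5 schedules a microscopic examination before the Day 15 application but places the Brighton grading 60 minutes after it. Confirm that a pre-application grade is recorded; if not, the Day 1 post-dose row is the only balanced scheduled Brighton comparison.
4. State that the whole-period tables describe the treat-until-closure regimen, and that the second- and third-dose rows are not randomised comparisons.
5. Events per application may be shown as a supportive descriptive figure, with the caveat that the denominator depends on closure and that active risk is overstated if events do not depend on repeat applications. The conclusion should not rest on it.

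Cost: SAP wording, one added TEAE/AESI display and one changed interval, settled before unblinding. The TEAE/AESI display uses AE onset and dosing data already collected, and no dosing rule changes. Downside: about two weeks of follow-up in the added table and low precision at 13 per arm.
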